5.6.3.9. Procedures for Ocular Manifestations

An ophthalmology consult should be considered. Administer corticosteroid eye drops to subjects who develop uveitis, iritis, or episcleritis. Permanently discontinue epacadostat and durvalumab for immune-mediated ocular disease that is unresponsive to local immunosuppressive therapy. The use of systemic immunosuppressive therapy may be appropriate for worsening ocular disease.

5.6.3.10. Procedures and Guidelines for Myocarditis

Table 18 provides recommendations for the management of suspected and confirmed myocarditis.

Table 18: Recommended Approach to Handling Myocarditis

Toxicity Grade	Withhold/Discontinue Epacadostat and Durvalumab	Guidance for Restarting Study Treatment	Supportive Care
Any	Discontinue study treatment permanently if biopsy-proven immune-mediated myocarditis.	Not applicable.	
 • The prompt diagnosis of immune-mediated myocarditis is important, particularly in patients with baseline cardiopulmonary disease and reduced cardiac function. • Consider, as necessary, discussing with the medical monitor. • Monitor patients for signs and symptoms of myocarditis (new onset or worsening chest pain, arrhythmia, shortness of breath, peripheral edema). As some symptoms can overlap with lung toxicities, simultaneously evaluate for and rule out pulmonary toxicity as well as other causes (eg, pulmonary embolism, congestive heart failure, malignant pericardial effusion). • A cardiology consultation should be obtained early, with prompt assessment of whether and when to complete a cardiac biopsy, including any other diagnostic procedures. • Initial work-up should include clinical evaluation, BNP, cardiac enzymes, ECG, ECHO, monitoring of oxygenation via pulse oximetry (resting and exertion), and additional laboratory work-up as indicated. Spiral CT or cardiac MRI can complement ECHO to assess wall motion abnormalities when needed. • Patients should be thoroughly evaluated to rule out any alternative etiology (eg, disease progression, other medications, or infections).
Grade 1	No dose modifications required unless clinical suspicion is high, in which case hold study treatment during diagnostic work-up for other etiologies.	If study treatment is held, resume after complete resolution to Grade 0.	
 • Monitor and closely follow up in 2-4 days for clinical symptoms, BNP, cardiac enzymes, ECG, ECHO, pulse oximetry (resting and exertion), and laboratory work-up as clinically indicated. • Consider using steroids if clinical suspicion is high.

Table 18: Recommended Approach to Handling Myocarditis (Continued)

Toxicity Grade	Withhold/Discontinue Epacadostat and Durvalumab	Guidance for Restarting Study Treatment	Supportive Care
Grade 2 or greater	
 • Grade 2: Hold study drug/study regimen dose until resolution to Grade 0. If toxicity rapidly improves to Grade 0, then the decision to reinitiate study drug/study regimen will be based upon treating physician’s clinical judgment and after completion of steroid taper. If toxicity does not rapidly improve, permanently discontinue study drug/study regimen. • Grade 3-4: Permanently discontinue study treatment 	
 • Grade 2 only: 
 – If toxicity rapidly improves to Grade 0, then the decision to reinitiate study treatment after steroid taper will be up to investigator’s clinical judgment. – If toxicity does not rapidly improve, permanently discontinue study treatment 	
 • Monitor symptoms daily, hospitalize. • Promptly start IV methylprednisolone 2-4 mg/kg per day or equivalent after cardiology consultation has determined whether and when to complete diagnostic procedures including a cardiac biopsy. • Supportive care (eg, oxygen). • If no improvement within 3-5 days despite IV methylprednisolone at 2-4 mg/kg per day, promptly start immunosuppressive therapy such as TNF inhibitors (eg, infliximab at 5 mg/kg every 2 weeks). Caution: It is important to rule out sepsis and refer to infliximab label for general guidance before using infliximab. • Once the patient is improving, gradually taper steroids over ≥ 28 days and consider prophylactic antibiotics, antifungals, or anti-PJP treatment (refer to current NCCN Guidelines for treatment of cancer-related infections [Category 2B recommendation])

5.6.3.11. Procedures and Guidelines for Myositis/Polymyositis

Table 19 provides recommendations for the management of myositis/polymyositis.

Table 19: Recommended Approach to Handling Myositis/Polymyositis

Toxicity Grade	Withhold/Discontinue Epacadostat and Durvalumab	Guidance for Restarting Study Treatment	Supportive Care
Any	Refer to guidance for specific grades below.	Not applicable.	
 • Monitor patients for signs and symptoms of myositis/polymyositis (poly/myositis). Typically, muscle weakness/pain occurs in proximal muscles, including upper arms, thighs, shoulders, hips, neck, and back but rarely affects the extremities, including hands and fingers; also difficulty breathing and/or trouble swallowing can occur and progress rapidly. Increased general feelings of tiredness and fatigue may occur, and there can be new-onset falling, difficulty getting up from a fall, and trouble climbing stairs, standing up from a seated position, and/or reaching up. • Consider, as necessary, discussing with the medical monitor, • If poly/myositis is suspected, a neurology consultation should be obtained early, with prompt guidance on diagnostic procedures. 
 – Myocarditis may co-occur with poly/myositis; refer to guidance under Section 5.6.3.10. – Given breathing complications, refer to guidance under Section 5.6.3.1. – Given possibility of an existent (but previously unknown) autoimmune disorder, consider rheumatology consultation. • Initial work-up should include clinical evaluation, creatine kinase, aldolase, LDH, BUN/creatinine, erythrocyte sedimentation rate or C-reactive protein level, urine myoglobin, and additional laboratory work-up as indicated, including a number of possible rheumatological/antibody tests (ie, consider whether a rheumatologist consultation is indicated and could guide the need for rheumatoid factor, antinuclear antibody, anti-smooth muscle, antisyntetase [such as anti-Jo-1], and/or signal-recognition particle antibodies). Confirmatory testing may include electromyography, nerve conduction studies, an MRI of the muscles, and/or a muscle biopsy. Consider barium swallow for evaluation of dysphagia or dysphonia. • Patients should be thoroughly evaluated to rule out any alternative etiology (eg, disease progression, other medications, or infections).

Table 19: Recommended Approach to Handling Myositis/Polymyositis (Continued)

Toxicity Grade	Withhold/Discontinue Epacadostat and Durvalumab	Guidance for Restarting Study Treatment	Supportive Care
Grade 1	No dose modifications	Not applicable.	
 • Monitor and closely follow up in 2-4 days for clinical symptoms and initiate evaluation as clinically indicated. • Consider a neurology consult. • Consider, as necessary, discussing with the medical monitor.
Grade 2	Hold study treatment	
 • Restart study treatment when resolved to \leq Grade 1. • Permanently discontinue study treatment if it does not resolve to \leq Grade 1 within 30 days or if there are signs of respiratory insufficiency. 	
 • Monitor symptoms daily and consider hospitalization. • Obtain a neurology consult, and initiate evaluation. • Consider, as necessary, discussing with the medical monitor. • If clinical course is rapidly progressive (particularly if difficulty breathing and/or trouble swallowing), promptly start IV methylprednisolone 2-4 mg/kg per day systemic steroids along with receiving input from the neurology consultant. • If clinical course is not rapidly progressive, start systemic steroids (eg, prednisone 1-2 mg/kg per day PO or IV equivalent); if no improvement within 3-5 days, continue additional work-up and start treatment with IV methylprednisolone 2-4 mg/kg per day. • If after start of IV methylprednisolone at 2-4 mg/kg per day there is no improvement within 3-5 days, consider start of immunosuppressive therapy such as TNF inhibitors (eg, infliximab at 5 mg/kg every 2 weeks). Caution: It is important to rule out sepsis and refer to infliximab label for general guidance before using infliximab. • Once the patient is improving, gradually taper steroids over \geq 28 days and consider prophylactic antibiotics, antifungals, or anti-PJP treatment (refer to current NCCN Guidelines for treatment of cancer-related infections [Category 2B recommendation]).

Table 19: Recommended Approach to Handling Myositis/Polymyositis (Continued)

Toxicity Grade	Withhold/Discontinue Epacadostat and Durvalumab	Guidance for Restarting Study Treatment	Supportive Care
Grade 3 or Grade 4	
 • Grade 3: Hold study treatment • Grade 4: Permanently discontinue study treatment 	
 • Grade 3 only: 
 – Restart study treatment when resolved to \leq Grade 1. – Permanently discontinue study treatment if it does not resolve to \leq Grade 1 within 30 days or if there are signs of respiratory insufficiency. 	
 • Monitor symptoms closely; recommend hospitalization. • Obtain a neurology consult, and complete full evaluation. • Consider, as necessary, discussing with the medical monitor. • Promptly start IV methylprednisolone 2-4 mg/kg per day systemic steroids along with receiving input from the neurology consultant. • If after start of IV methylprednisolone at 2-4 mg/kg per day there is no improvement within 3-5 days, consider start of immunosuppressive therapy such as TNF inhibitors (eg, infliximab at 5 mg/kg every 2 weeks). Caution: It is important to rule out sepsis and refer to infliximab label for general guidance before using infliximab. • Consider whether patient may require IVIG, plasmapheresis. • Once the patient is improving, gradually taper steroids over \geq 28 days and consider prophylactic antibiotics, antifungals, or anti-PJP treatment (refer to current NCCN Guidelines for treatment of cancer-related infections [Category 2B recommendation]).

5.6.3.12. Procedures for Immune-Related Adverse Events Not Specifically Described Above

Table 20 provides information on the diagnosis and treatment of potential irAEs.

Table 20: General Guidance for Diagnosis and Treatment of Immune-Related Adverse Events (Not Described in Previous Sections)

Subject evaluation to identify any alternative etiology
In the absence of a clear alternative etiology, all events of inflammatory nature should be considered to be immune-related
Symptomatic and topical therapy should be considered for low-grade events
Systemic corticosteroids should be considered for a persistent low-grade event or for a severe event
More potent immunosuppressives should be considered for events not responding to systemic steroids

In general, both study drugs should be permanently discontinued for clinically significant or severe irAEs or for events where the steroid course cannot be tapered below 10 mg/day prednisone equivalent to manage symptoms. Following an irAE where treatment was withheld, study treatment may resume when the following conditions are met: steroid taper has reached \leq 10 mg/day prednisone or equivalent, symptoms have improved to \leq Grade 1 within 4 weeks of

onset (or longer with medical monitor approval), and, as appropriate, physiologic replacement of hormones has been instituted. Additional treatment regarding modifications to study drug administration for irAEs is detailed in [Table 21](#).

Table 21: Recommended Approach for Handling Immune-Related Adverse Events (Not Described in Previous Sections)

Toxicity Grade	Withhold/Discontinue Epacadostat and Durvalumab	Guidance for Restarting Study Treatment
Grade 1	No action.	Not applicable.
Grade 2	Withhold epacadostat and durvalumab. If toxicity worsens, treat as Grade 3 or Grade 4. Subjects with endocrinopathies who may require prolonged or continued steroid replacement can be re-treated with study treatment on the following conditions: 1) the event stabilizes and is controlled, 2) the subject is clinically stable as per investigator or treating physician’s clinical judgement, and 3) doses of prednisone are at ≥ 10 mg/day or equivalent. Consider whether study drug/study regimen should be permanently discontinued in Grade 2 events with high likelihood for morbidity and/or mortality (eg, myocarditis, or other similar events even if they are not currently noted in the guidelines) when they do not rapidly improve to $<$ Grade 1 upon treatment with systemic steroids and following full taper.	Resume study treatment at same dose/schedule when AE resolves to \leq Grade 1 or baseline.
Grade 3	Discontinue epacadostat and durvalumab (exceptions to this approach allowing study treatment to continue after resolution of the AE may be granted only with medical monitor approval).	Not applicable (unless approved by the medical monitor).
Grade 4	Discontinue epacadostat and durvalumab. Note: There are some exceptions to permanent discontinuation of study drug for Grade 4 events (ie, hyperthyroidism, hypothyroidism, Type 1 DM).	Not applicable (unless approved by the medical monitor).

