20. History or presence of an abnormal ECG that, in the investigator's opinion, is clinically meaningful. Screening QTc interval > 480 msec is excluded (corrected by Fridericia or Bazett's formula). In the event that a single QTc is > 480 msec, the subject may be enrolled if the average QTc for the 3 ECGs is \leq 480 msec. For subjects with an intraventricular conduction delay (QRS interval \geq 120 msec), the JTc interval may be used in place of the QTc with sponsor approval. The JTc must be < 340 msec if JTc is used in place of the QTc. Subjects with left bundle branch block are excluded.
21. Clinically significant cardiac disease, including unstable angina, acute myocardial infarction within 6 months from Day 1 of study drug administration, New York Heart Association Class III or IV congestive heart failure, and arrhythmia requiring therapy.
- Note: A subject with an arrhythmia may enroll if the subject is on anti-arrhythmic medication and is in sinus rhythm on the screening ECG.*
22. Any prior \geq Grade 3 irAE while receiving immunotherapy, including anti-PD-1, anti-PD-L1, or anti-CTLA-4 treatment, or any unresolved irAE > Grade 1. Must not have experienced a toxicity that led to permanent discontinuation of prior immunotherapy. Subjects with endocrine AEs \leq Grade 2 are permitted to enroll if they are stably maintained on appropriate replacement therapy and are asymptomatic. Subjects with prior anti-PD-1, anti-PD-L1, or anti-CTLA-4 therapy must not have required the use of additional immunosuppression other than corticosteroids for the management of an AE, not have experienced recurrence of an AE if rechallenged, and not currently require maintenance doses of > 10 mg prednisone or equivalent per day.
- Note: Previous immune-related ocular or neurologic toxicity of any grade is excluded.*
23. Known allergy or reaction to any component of either study drug formulation.
24. Subjects who require ongoing thoracentesis or paracentesis for palliation must be discussed with the medical monitor to determine eligibility.
25. History of primary immunodeficiency.
26. History of leptomeningeal carcinomatosis.

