5.6.3. Criteria for Subjects Exhibiting Immune-Related Adverse Events

This section is meant to apply to suspected irAEs from epacadostat, durvalumab, or the combination. Immune-related AEs may be predicted based on the nature of the durvalumab or epacadostat compounds, their mechanism of action, and reported experience with immunotherapies that have a similar mechanism of action. Special attention should be paid to AEs that may be suggestive of potential irAEs. An irAE can occur shortly after the first dose or several months after the last dose of treatment.

If an irAE is suspected, efforts should be made to rule out neoplastic, infectious, metabolic, toxin, or other etiologic causes prior to labeling an AE as an irAE. Subjects who develop a \geq Grade 2 irAE should be discussed immediately with the medical monitor.

Recommendations for management of specific immune-mediated AEs such as pneumonitis (see Section 5.6.3.1), enterocolitis (see Section 5.6.3.2), hepatitis (see Section 5.6.3.3), dermatitis (see Section 5.6.3.4), immune-mediated neuropathies (see Section 5.6.3.5), immune-mediated endocrinopathies (see Section 5.6.3.6), immune-mediated nephritis or renal dysfunction (see Section 5.6.3.7), and ocular manifestations (see Section 5.6.3.8) are detailed in the sections below.

General recommendations to managing irAEs not detailed elsewhere in this section are detailed in Section 5.6.3.12.

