Grade 2	For endocrinopathy other than hypothyroidism, withhold epacadostat and durvalumab.	
If study treatment is held, resume study treatment at same dose/schedule until subject is clinically stable.
 
 • If toxicity worsens, then treat as Grade 3 or Grade 4. • Study treatment can be resumed once the event stabilizes and after completion of steroid taper. • Subjects with endocrinopathies who may require prolonged or continued steroid replacement can be re-treated with study treatment on the following conditions: 1) the event stabilizes and is controlled, 2) the subject is clinically stable as per investigator or treating physician's clinical judgement, and 3) doses of prednisone are at ≤ 10 mg/day or equivalent. 	
 • Consult endocrinologist to guide evaluation of endocrine function, and as indicated by suspected endocrinopathy and as clinically indicated, consider pituitary scan. • Isolated hypothyroidism may be treated with replacement therapy without treatment interruption and without corticosteroids. • Isolated Type 1 DM may be treated with appropriate diabetic therapy, without study drug interruption, and without corticosteroids. • For subjects with abnormal endocrine work-up, except for those with isolated hypothyroidism, consider short-term, high-dose corticosteroids (eg, methylprednisolone 1-2 mg/kg per day or IV equivalent) and initiate appropriate hormone replacement therapy. • Once improving, gradually taper steroids over ≥ 28 days and consider prophylactic antibiotics, antifungals, and anti-PCP treatment (refer to current NCCN Guidelines for treatment of cancer-related infections [Category 2B recommendation]). • For subjects with normal endocrine work-up (labs or MRI), repeat labs/MRI as clinically indicated.

Table 15: Recommended Approach for Handling Endocrinopathies (Continued)

Toxicity Grade	Withhold/Discontinue Epacadostat and Durvalumab	Guidance for Restarting Study Treatment	Supportive Care

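### Table 21 reverses the steroid limit for restarting treatment in subjects with endocrinopathies: it asks for at least 10 mg/day of prednisone where the rest of the protocol asks for at most 10 mg/day

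*Protocol*

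**What the plan says.** Three places in the protocol give a steroid dose for resuming study treatment after an immune-related adverse event (irAE).

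- **Section 5.6.3.6, Table 15 (Grade 2 endocrinopathies).** Subjects who may need prolonged steroid replacement can be re-treated if the event is stable and controlled, the subject is clinically stable, and "doses of prednisone are at ≤ 10 mg/day or equivalent".
- **Section 5.6.3.12, text above Table 21.** "Following an irAE where treatment was withheld, study treatment may resume when the following conditions are met: steroid taper has reached" 10 mg/day of prednisone or less. Symptoms must also have improved to Grade 1 or better within 4 weeks of onset (longer with medical monitor approval), and hormones must have been replaced where appropriate. The sentence before it says both drugs should in general be stopped for good when steroids cannot be tapered below 10 mg/day.
- **Section 5.6.3.12, Table 21 (Grade 2 row).** The Table 15 conditions are repeated for subjects with endocrinopathies, but the third reads "doses of prednisone are at ≥ 10 mg/day or equivalent".

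Section 5.6.3 says which section applies. It points to "immune-mediated endocrinopathies (see Section 5.6.3.6") for these events and states "General recommendations to managing irAEs not detailed elsewhere in this section are detailed in Section 5.6.3.12". It also says that a subject with a Grade 2 or higher "irAE should be discussed immediately with the medical monitor".

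**The concern.** The sentence in Table 21 is a decision rule for restarting two immune-activating drugs after a Grade 2 immune-related event. A minimum steroid dose makes no sense as a condition for restarting. The purpose of such a threshold is to show that the event is controlled without immunosuppressive doses, which calls for a ceiling.

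A site that uses the Table 21 row finds written permission to restart at prednisone doses above 10 mg/day, with no upper limit. Section 1.3.3 warns that the combination may cause more frequent, more severe or new immune-related toxicities compared with each drug alone, so the direction of this threshold matters. Sites and monitors are also left without a single standard for deciding whether a restart was a protocol deviation.

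**Working it through.** No arithmetic applies. The check is to compare the rules, see where they disagree, and ask which direction the rest of the protocol supports.

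**1. The rules at three doses.** The doses of 5 and 20 mg/day are illustrations on either side of the threshold. Only the steroid condition is tested; the other conditions are taken as met.

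| Prednisone dose | Table 15 (at most 10) | Section 5.6.3.12 text (at most 10) | Table 21 (at least 10) |
|---|---|---|---|
| 5 mg/day | may restart | may restart | condition not met |
| 10 mg/day | may restart | may restart | may restart |
| 20 mg/day | condition not met | condition not met | may restart |

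The rules overlap at exactly 10 mg/day and nowhere else. Two of the three make 10 mg/day a maximum; one makes it a minimum.

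**2. Which disagreement carries the risk.** Below 10 mg/day, Table 21 on its own would hold back a subject whom the other two rules clear. That error is cautious, and such a subject has an explicit route to restart under Table 15 and the text. Above 10 mg/day, Table 21 permits what the other two rules forbid. The safety problem lies there.

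**3. Which sign is intended.**

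- The text immediately above Table 21 uses the maximum, and treats failure to taper below 10 mg/day as a general reason to stop both drugs permanently. The table cannot sensibly require what that paragraph gives as grounds for stopping.
- Section 5.10.1 restricts systemic steroids to 10 mg/day or less, with medical monitor approval.
- Section 3.3, exclusion criterion 22, requires that subjects with prior checkpoint therapy do "not currently require maintenance doses of > 10 mg prednisone or equivalent per day". This is an entry rule, not a restart rule, so it is weaker support, but it uses 10 mg/day in the same direction.
- Section 5.10.2 does allow 10 mg/day or more with medical monitor approval, but for treating immune-related toxicities. It is a concomitant-medication allowance and does not explain a minimum dose for restarting study drug.

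No passage was found that gives a reason for a minimum dose. The Table 21 sentence matches the Table 15 sentence apart from the sign, which suggests a copying error.

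**The case against.** The strongest reply is that several safeguards would have to fail before anyone was harmed. Endocrinopathies are routed to Table 15. The titles of Section 5.6.3.12 and Table 21 confine them to events not described earlier. The paragraph above Table 21 states the correct ceiling. Grade 2 or higher events should be discussed with the medical monitor at once, and Section 5.10 requires that monitor's approval for systemic steroids, so a subject above 10 mg/day should already be known. The row also keeps its other conditions: event controlled, subject clinically stable, and, in the restart column, resolution to Grade 1 or baseline. On this view the slip is editorial.

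Most of this stands and limits the severity. It does not remove the conflict. Table 21 names subjects with endocrinopathies, so its sentence reads as live guidance for them despite the routing. Discussion with the medical monitor is not a steroid ceiling, and the monitor would be reading the same two tables. The remaining conditions do not limit the dose.

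A second reply is that the point turns on one symbol in a table read from a PDF, and a reading error cannot be fully excluded. That is fair. The text does show different signs in otherwise matching sentences, and the sponsor can settle it by looking at the source page.

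**Conclusion.** The concern holds. Table 21 contradicts Table 15 and the text of its own section, and the protocol as a whole shows that 10 mg/day was meant as a maximum. The conflict that matters covers every prednisone dose above 10 mg/day. The number of subjects who might be restarted on such doses cannot be estimated, because the documents give no rate for Grade 2 endocrinopathies needing prolonged steroids on this combination.

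This is an internal inconsistency in safety guidance that should be fixed. It has no effect on the objective response rate, the sample sizes, the error rates or any planned analysis. The conclusion assumes that the sign in the source document is as it appears in the extracted text.

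**What to change.** In the Grade 2 row of Table 21, change the condition from at least 10 mg/day to at most 10 mg/day. Alternatively, delete the endocrinopathy sentence from that row and refer to Table 15, which leaves one rule in one place. Send sites a clarification letter so that the correction takes effect without waiting for an amendment.

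The cost is one character, or one deleted sentence, and one letter. Design, data collection and analysis do not change.
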